3.2.1 Subjects of assessment

All study subjects in the 8 study groups.

3.2.2 Assessment time

The assessment time for the study subjects should be from the first implementation of the intervention activities, when 6 months are completed (the control assessment time is within \pm 7 days) to implement the first effect assessment.

3.2.3 Assessment content

The content of the assessment includes: fall-related knowledge, attitude and behaviour, daily life ability and fall efficacy.

3.2.4 Assessment methods and tools

The same assessment methods and tools as the baseline survey (Annex 5, Part IV, Part V and Part VI).

3.3 Second Effectiveness Assessment (at 12 months after the commencement of the first intervention)

3.3.1 Subjects to be assessed

All study subjects in the 8 study groups.

3.3.2 Assessment time

The assessment time for the study subjects should be from the first implementation of the intervention activities, when 12 months are completed (the control assessment time is within \pm 7 days) to implement the second effect assessment.

3.3.3 Assessment content

The content of the assessment includes: the same as the baseline survey ("Annex 5, Part III, Falls" does not need to be surveyed).

3.3.4 Assessment methods and tools

The same assessment methods and tools as the baseline survey.

(4) Economics Evaluation

Targeted cost-effect and cost-utility analyses from a social perspective will help evaluate the real effects of the interventions in preventing falls in old age, and provide a data basis for the governmental decision-making authorities to formulate reasonable intervention policies.

4.1 Municipal Project Office

4.1.1 Collection time

After 6 months of intervention (after the end of the 6-month evaluation) and 12 months (after the end of the 12-month evaluation).

4.1.2 Collection content

The municipal project office intervention cost collection mainly includes the direct

costs and time invested to carry out the falls intervention programme. Direct costs mainly include travel costs for training, venue costs, expert costs, programme and manual production costs, and survey tool costs. The time invested in carrying out the falls intervention project includes the time invested by the municipal project office in designing and preparing the project, initiating and managing the project, carrying out the first level of training, attending the second level of training, and supervising the work.

4.1.3 Collection method

The main person in charge of the project in the municipal project office will fill in the "Questionnaire on Workload and Cost Expenditure of Falls Intervention Project for the Elderly in the Municipal Project Office" (Appendix 10) on his/her own, taking into account the details of the financial expenditures.

4.2 District-level project offices

4.2.1 Collection time

Intervention full 6 months (6 months after the end of the assessment) and 12 months (12 months after the end of the assessment).

4.2.2 Collection of content

The district-level project office intervention cost collection mainly includes the direct cost of expenditure and time invested to carry out the falls intervention programme. Direct costs include questionnaires, measurement tools, home environment improvement supplies, and labour costs. The time invested in carrying out the falls intervention programme includes the time invested in attending the primary training, carrying out the secondary training, recruiting/screening older people in the community, conducting the baseline survey, implementing the intervention, evaluating the process, and evaluating the effects.

4.2.3 Method of collection

The main person in charge of the project in the district-level project office will fill in the "Questionnaire on Workload and Cost Expenditure of Elderly Falls Intervention Project in District-level Project Office" (Annex 11) by himself/herself in conjunction with the breakdown of financial expenditure.

4.3 Primary health care institutions

4.3.1 Collection time

Intervention full 6 months (6 months after the end of the assessment) and 12 months (12 months after the end of the assessment).

4.3.2 Collection content

The primary project office intervention cost collection mainly includes the direct cost of expenditure and time invested in carrying out the falls intervention programme. Direct costs mainly include printing questionnaires, purchasing measurement tools and supplies for home environment improvement, and labour costs. The time invested in the falls intervention programme included the time invested in attending Level 1 and Level 2 trainings, recruiting/screening older people in the community, conducting baseline surveys, implementing interventions, and evaluating outcomes.

4.3.3 Method of collection

The main person in charge of the project in the grassroots project office, together with the breakdown of financial expenditure, filled in the "Questionnaire on Workload and Cost Expenditure of Falls Intervention Programme for the Elderly in the Grassroots Project Office" on his/her own (Annex 12).

4.4 Collection of Costs Related to Research Subjects

4.4.1 Collection time

From the beginning of the intervention to the end of the endline assessment, collected on a monthly basis (accompanied by a monthly calendar of falls).

4.4.2 Collection content

Costs related to falls of the study participants mainly include outpatient/emergency room visits, hospitalisation costs, drug costs, nutritional costs, home care and carer/nanny costs due to falls during the project period.

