resources and costs; furthermore, the study will provide scientific references and practical tools for the city to carry out the fall intervention services for the elderly applicable to the primary healthcare institutions, and ultimately reduce the incidence of falls among the elderly, and improve the quality of their lives.

II. Objectives of the Study

(1) General objectives of the study

Using a multi-stage optimisation strategy, the group will optimise the project intervention programme in the improvement phase, conduct a randomised controlled trial using a factorial design, quantitatively compare the effects of different falls programmes on falls prevention, carry out an economic evaluation of the different intervention groups, and ultimately determine the optimal combination of intervention strategies for the project. To explore and establish a community-based falls prevention intervention model for the elderly, and to provide a scientific basis and a practical tool for the establishment of a community-based falls prevention service model for the elderly that is suitable for implementation by primary healthcare organisations in the city. Ultimately, through city-wide dissemination and implementation, we will achieve the goal of reducing the incidence of falls among older adults and improving their quality of life.

(2) Specific objectives

1. To be achieved through a 2-month intervention for the target population within 12 months after the start of the implementation of the intervention:

1.1 Apply a multi-stage optimisation strategy, centred on an analytic design randomised controlled trial, to screen for elements of a community falls prevention intervention for older people and optimise a comprehensive intervention management strategy for community falls prevention in older people;

1.2 Evaluate the inputs and outputs of the multifactorial intervention strategy for the prevention of falls in older people, to provide a basis for the dissemination of the intervention strategy and government decision-making.

III. Study subjects

The researcher used the Screening Form for Research Subjects (Annex 2) to select eligible elderly people as research subjects among the elderly population by means of questionnaires and scale assessments.

(1) Study subjects

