1.2 Duration and intensity of intervention

60 minutes/time, once in each of the 1st, 3rd, 5th and 8th weeks of the intervention period.

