2.2 Duration and intensity of intervention

30 minutes/time, once in each of the 1st, 3rd, 5th and 8th weeks of the intervention period.

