4.4.3 Collection method

The staff of the grassroots project office used the "Questionnaire on Falls-Related Expenses during the Intervention Period of the Study Subjects" (Appendix 13), which was obtained through face-to-face surveys, combined with the data from the elderly's medical expenditure records and financial documents.

As different types of expenses may be incurred by a particular fall of the study participant, when completing the "Questionnaire on Falls-related Expenses during the Intervention Period of the Study Participants" (Annex 13), staff members filled in the corresponding questionnaire in Annex 13 according to the different treatments actually incurred by the study participant. Possible treatment situations include self-treatment (Part I of Annex 13), outpatient emergency visit (Part II of Annex 13), inpatient treatment (Part III of Annex 13), out-of-hospital rehabilitation treatment (Part IV of Annex 13), and review (Part V of Annex 13). In case of inpatient treatment for study subjects, the final cost was entered at the time of discharge. The information collected is not duplicated with that collected in the previous month. If the study participant had rehabilitation treatment, rehabilitation in outpatient emergency clinic was counted in the outpatient

emergency clinic fee schedule (Annex 13 Part II), rehabilitation during inpatient hospitalisation was counted in the total inpatient hospitalisation fee (Annex 13 Part III), and out-of-hospital rehabilitation was counted in the out-of-hospital rehabilitation fee (Annex 13 Part IV).

VII. Methods of Statistical Analysis

(1) Data collection

The collection and management of all research data will be done relying on the REDCap platform. After the formation of the preliminary database, the database will be checked and cleaned again for logical errors and missing values, and the database will be finally formed after further verification and correction by telephone follow-up with the respondents.

(2) Data collation and analysis

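### The economic evaluation is labelled social, but no cost item described covers what the components themselves cost participants, and that omission differs by component

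*Combined protocol and SAP*

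**What the plan says.** The general objective in Section II (1) is to "carry out an economic evaluation of the different intervention groups, and ultimately determine the optimal combination of intervention strategies for the project". Specific objective 1.2 speaks only of inputs and outputs. The perspective is set in Section VI (4), Economics Evaluation: "Targeted cost-effect and cost-utility analyses from a social perspective". Section VII (2) adds that an ICER will be used, without naming a comparator.

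Sections 4.1.2, 4.2.2 and 4.3.2 collect direct costs and staff time from the municipal, district and primary-care offices. The district and primary-care lists include home-improvement supplies.

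Section 4.4 is the only participant-side collection. Its content is "Costs related to falls of the study participants mainly include outpatient/emergency room visits, hospitalisation costs, drug costs, nutritional costs, home care and carer/nanny costs". Its form is the "Questionnaire on Falls-Related Expenses during the Intervention Period of the Study Subjects" (Annex 13). Section 4.4.3 describes the parts of that form: "Possible treatment situations include self-treatment (Part I of Annex 13), outpatient emergency visit (Part II of Annex 13), inpatient treatment", followed by out-of-hospital rehabilitation and review.

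The components ask the following of participants:
- Education (Section V (1), 1.2): "60 minutes/time, once in each of the 1st, 3rd, 5th and 8th weeks of the intervention period".
- Exercise (Section V (2), 2.2): "30 minutes/time, once in each of the 1st, 3rd, 5th and 8th weeks of the intervention period".
- Environment (Section V (3), 3.1 and 3.2.1): one home visit of unstated length, with written modification advice and a minimum package of supplied items.

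**The concern.** A social perspective counts costs whoever bears them, including participants' time and their own spending. The plan counts the time of the staff who run a session but describes no item for the time of the participants who attend it. It counts the items the project supplies for the home, but describes no item for what a household pays to follow the rest of the advice.

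This matters because the economic evaluation is meant to help select a combination of components. A cost left out equally from all eight groups would drop out of every incremental comparison. This one is zero in Group 5 and differs among the active components, so it stays in the differences from which an ICER is built. Readers would then take as social an ICER that omits a cost the label implies.

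**Working it through.** The plan states no figure for participant cost, so there is none to reproduce. The check has two parts.

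**1. Cost headings against the stated perspective**

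| Cost | Described in Section VI (4)? |
|---|---|
| Office direct costs and staff time | Yes (4.1.2, 4.2.2, 4.3.2) |
| Supplied home-improvement items | Yes, as provider cost (4.2.2, 4.3.2) |
| Treatment and care after a fall | Yes (4.4.2, 4.4.3) |
| Participant time in sessions | No |
| Participant travel to sessions | No |
| Participant time at the home visit | No |
| Household spending beyond the supplied items | No |
| Participant's lost time after a fall | Not listed |

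**2. Size of the omitted contact time**

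Inputs from the documents:
- education 4 × 60 min = 4 h; exercise 4 × 30 min = 2 h (Section V);
- 111 participants per group (Section III (2));
- group composition (Table 1).

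Assumption: the home visit lasts H hours, with H between 0.5 and 1.5. The documents give no length.

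Hours per participant at full attendance, before travel:

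| Group | 1 | 2 | 3 | 4 | 5 | 6 | 7 | 8 |
|---|---|---|---|---|---|---|---|---|
| Hours | 6 + H | 6 | 4 + H | 4 | 0 | 2 + H | 2 | H |

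Component contrast = mean of the four groups with the component minus mean of the four without:
- education: (20 + 2H)/4 − (4 + 2H)/4 = 4 h;
- exercise: (16 + 2H)/4 − (8 + 2H)/4 = 2 h;
- environment: (12 + 4H)/4 − 12/4 = H, that is 0.5 to 1.5 h.

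Trial total = 111 × (24 + 4H) = 2,664 + 444H. This is 2,886 h at H = 0.5 and 3,330 h at H = 1.5. Education contributes 444 × 4 = 1,776 h and exercise 444 × 2 = 888 h.

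*Travel.* Assume a round trip of 30 to 60 min per session date, with one trip serving both components where a group has both, since they meet in the same weeks. Every education group makes 4 trips. The groups without education average 2 (Groups 6 and 7 make 4, Groups 5 and 8 none). The contrast is 2 trips, or 1 to 2 h, and the same holds for exercise. The contrasts become 5 to 6 h for education and 3 to 4 h for exercise, so the ratio falls from 2 to between 5/3 = 1.7 and 6/4 = 1.5.

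*Scale per faller averted, illustration only.* The sample-size section uses 17% incidence and a 35% reduction: 0.17 × 0.35 = 0.0595, and 1/0.0595 = 16.8 participants per faller averted. If a component achieved that effect alone with full attendance, the uncounted contact time per faller averted would be:
- education: 4/0.0595 = 67 h;
- exercise: 2/0.0595 = 34 h;
- environment: 0.5/0.0595 to 1.5/0.0595 = 8 to 25 h.

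**The case against.** A reader might infer that every ICER against Group 5 is too favourable, or that the components cannot be compared fairly. The documents do not support either statement.

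- **Direction.** Sections 4.4.2 and 4.4.3 list no lost time for the person who falls. If that is also left out, the savings from prevented falls are undercounted, which pushes the other way. The net sign is open. Group 5 is also not named as the ICER comparator.
- **Fair comparison.** Session lengths are fixed, attendance is logged in Annex 3 (Section VI (2), 2.3.1), and the time of the home assessment is recorded (Section V (3), 3.4). For contact time, what is missing is a valuation step rather than data. A provider-perspective comparison is untouched, and it is useful in its own right because the plan seeks a model that primary care can deliver.
- **Money.** No unit value of time is given, so the hours cannot be turned into a change in any ICER or in the ranking of components. Household spending has no figure at all, and the supplied package already covers part of it.
- **Completeness.** The list in 4.4.2 is worded as the main items rather than all of them, and the annexes are not shown. The claim has to be that no item described covers these costs.

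All four points stand as limits. None of them gives the costing the perspective it claims: the list in 4.4.2 and every described part of Annex 13 concern falls, attendance is used only for process evaluation, and no source described would supply travel or household spending.

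**Conclusion.** The point holds as a mismatch between label and content. Section VI (4) states a social perspective, and the costs it describes are provider costs plus costs due to falls. The omitted scheduled session time is 4 h for education, 2 h for exercise and 0 h in Group 5, with one home visit of unstated length for environment. It therefore does not cancel between groups. Taken alone, it understates the cost of the active components, most of all education on session time.

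The net effect on the ICERs is unknown. The hours assume full attendance. The visit and travel ranges are assumptions. The per-faller figures also assume that each component alone achieves the 35% reduction, which the plan does not say. The falls outcome is not affected.

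**What to change.** Either of two changes resolves it.

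**Keep the social perspective and complete the costing.**
1. Value participant time as attendance recorded in Annex 3 times session length, plus the recorded home visit. State the unit value of time in advance and vary it in a sensitivity analysis.
2. Ask once, at the 12-month assessment and after the last fall calendar has been collected, about usual travel time and fare to sessions and about household spending on home modification. Place these questions after the other measurements.

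A monthly question beside the fall calendar would be worse. Section IX (7), 7.1 has falls assessed by staff who do not know the group, and answers about home changes could reveal it. Repeated asking could also prompt modification in the four groups without that component. It would mean up to 888 × 12 = 10,656 askings.

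**Or relabel.** Restate the perspective in Section VI (4) as provider cost plus fall-related cost, and do not call the ICERs social. This needs only a wording change and remains possible after fieldwork has ended.

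The first option costs one or two questions that rely on recall over 12 months, a short calculation, and somewhat higher component costs. The second gives up the social claim.

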4.4.3 Collection method

The staff of the grassroots project office used the "Questionnaire on Falls-Related Expenses during the Intervention Period of the Study Subjects" (Appendix 13), which was obtained through face-to-face surveys, combined with the data from the elderly's medical expenditure records and financial documents.

As different types of expenses may be incurred by a particular fall of the study participant, when completing the "Questionnaire on Falls-related Expenses during the Intervention Period of the Study Participants" (Annex 13), staff members filled in the corresponding questionnaire in Annex 13 according to the different treatments actually incurred by the study participant. Possible treatment situations include self-treatment (Part I of Annex 13), outpatient emergency visit (Part II of Annex 13), inpatient treatment (Part III of Annex 13), out-of-hospital rehabilitation treatment (Part IV of Annex 13), and review (Part V of Annex 13). In case of inpatient treatment for study subjects, the final cost was entered at the time of discharge. The information collected is not duplicated with that collected in the previous month. If the study participant had rehabilitation treatment, rehabilitation in outpatient emergency clinic was counted in the outpatient

emergency clinic fee schedule (Annex 13 Part II), rehabilitation during inpatient hospitalisation was counted in the total inpatient hospitalisation fee (Annex 13 Part III), and out-of-hospital rehabilitation was counted in the out-of-hospital rehabilitation fee (Annex 13 Part IV).

VII. Methods of Statistical Analysis

(1) Data collection

The collection and management of all research data will be done relying on the REDCap platform. After the formation of the preliminary database, the database will be checked and cleaned again for logical errors and missing values, and the database will be finally formed after further verification and correction by telephone follow-up with the respondents.

(2) Data collation and analysis

SPSS20.0 was used for statistical processing. Variables such as general demographic characteristics, disease characteristics, previous falls, and level of social support at baseline were compared to see if there were any differences between the different intervention groups, and variables with differences would be corrected in the subsequent analyses. Intent-to-treat (ITT) analysis is proposed to evaluate the intervention in this study. Descriptive analysis: statistical descriptions of primary outcome variables, secondary outcome variables, intervention implementation and other synergistic factors, etc., and independent samples t-tests (continuous variables such as Older Adult Falls Efficacy Scale scores, Quality of Life Scale scores, Older Adults' Falls Knowledge and Belief Behaviour Scale scores, etc.) and chi-square tests (categorical variables such as attitudes towards the intervention strategy, incidence of falls, etc.) to compare the between-groups differences were used.

The study proposes to assess the economic benefits using Incremental Cost-Effectiveness Ratio (ICER), which is the increased cost per unit of effect.

VIII. Safety Guarantee

- (1) When carrying out the various screening, assessment, training, exercise and other activities of the project, the safety and physical health of the research subjects should be ensured as the first principle.
- (2) During the various screening and assessment processes, research subjects should be clearly informed of the testing methods and possible risks. The project may conduct demonstrations and allow research subjects to practise before taking formal measurements. The staff should remind the participants that they should not pursue "good results" in the test.
- (3) In the process of training and exercise, the basic principles are gradual and according to one's ability, and research subjects should not be forced to perform movements that are beyond their ability. All exercises are subject to the subjective feeling of the research subjects themselves, while attention should be paid to correcting the research subjects' sense of "not obeying the old" and stopping dangerous actions in time.
- (4) When carrying out the assessment activities, the staff should clean up the risk factors in the environment beforehand, removing slippery ground, unevenness, obstacles and other environmental risk factors that may cause injuries to the research subjects. Seats or similar facilities for research subjects to rest should also be provided.
- (5) Staff should prepare first-aid medication and related equipment at all project sites, and staff who can administer primary first aid should be present at each site.

IX. Quality control

(1) Quality control of the process of formulating and developing the project programme and related intervention tools

At different stages, through the organisation of experts in different fields, work programmes such as the overall project programme, the survey and assessment programme, and the intervention implementation programme; the design and use of questionnaires, checklists and record forms for various types of surveys and assessments; and the content and form of interventions are validated.

(2) Quality control of data collection

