1.1.3 Requirements for the proportion of recruited subjects

In order to increase the homogeneity of study subjects, study subjects can be recruited with reference to the following gender and age requirements:

① 20% male, 80% female; ② 30%-35% aged 60-65 years, ③ 30%-35% aged 66-70 years, ④ 30%-35% aged 71-75 years, ⑤ less than 10% aged 76-80 years.

(2) Sample size estimation

After scientific calculations, combined with the actual work, a total of 888 people are needed for this project, then each group needs a sample size of $n=111$, and a total of 37 people are recruited in each street (town). The sample size calculation process is as follows:

This study uses the dichotomous variable "whether a fall occurs" as the outcome indicator. According to the results of the occurrence of falls among the elderly in the community in Guangzhou City in 2023, the incidence of falls among the elderly in Baiyun District was 17%. After discussion with experts, it was concluded that a 35% reduction in the incidence of falls after the intervention was considered to be of public health significance. In this study, the test level was set at $\alpha=0.05$ and the test efficacy at 0.8 (i.e., $\beta=0.2$). The proposed factorial design for this study is based on the sample size formula (below) for factorial designs in which the outcome variable is a dichotomous variable, and the sample size required for each test condition can be obtained as:

$$n = \frac{(Z_{1-\alpha/2} + Z_{1-\beta})^2}{2^k [\arcsin(\sqrt{\frac{\rho+\rho\delta}{2}}) - \arcsin(\sqrt{\frac{\rho-\rho\delta}{2}})]^2} \approx 83$$

$$\rho=0.17, \delta=0.35, Z_{1-\alpha/2}=1.96, Z_{1-\beta}=0.84, k=3.$$

The total sample size required for the 8 test conditions was:

$$N_{\text{conditions}} = 83 \times 8 = 664$$

According to S. Bhasin, T.M et al, the design effect of whole cluster randomisation can be obtained by estimating $ICC = 0.0076$ and mean number of individuals in the cluster $m = 28$:

$$DE = 1 + (m-1) \times ICC = 1 + (28-1) \times 0.0076 = 1.2052$$

The sample size was set to be the same for the eight test conditions, and the total sample size required for the study was:

$$N = N_{\text{conditions}} \times DE \div (1 - 10\%) \approx 888$$

The required sample size for each test condition was then 111 cases;

Each of the 24 streets recruited 37 study participants.

(3) Intervention groups

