1.2.5 Assessment methods and tools

① Assessment methods

Questionnaire survey, on-site observation and other methods are selected according

to different assessment contents.

② Assessment tools

Self-administered questionnaire: basic demographic information, physical activity, illness and medication use, and occurrence of falls (occurrence of falls in the last year);

Established scale measurements: Falls Effectiveness Scale for the Elderly, Quality of Life Scale.

See Annex 5 for specific assessment methods and tools.

Table 4 List of project baseline survey and assessment contents, methods and tools

Content		Method	Tool
classification	item		
Basic demographic information	Name, sex, age, address, contact details, ethnicity, level of education, living with the family, occupational status	Survey	Annex 5: Survey Assessment Form (Part I)
Illness, Medication and Medical conditions	Type and number of illnesses, type and number of medicines used	Survey	Annex 5: Survey Assessment Form (Part II)
Information about falls	Incidents of falls, history of falls	Survey	Annex 5: Survey Assessment Form (Part III)
	Falls Related Knowledge, Attitude and Action	Survey	Annex 5: Survey Assessment Form (Part IV)
	Falls efficacy	Scale	Annex 5: Survey Assessment Form (Part V)
Quality of Life Scale	Capacity for daily living	Scale	Annex 5: Survey Assessment Form (Part VI)
Gait	"Stand-up-and-walk" timing test	on-site test	Annex 5: Survey Assessment Form (Part VI I)

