2.4 Assessment Tools

Different assessment tools such as observation record sheets, questionnaires, interview outlines, etc. were selected and used according to the different contents and methods of the process assessment, as detailed in Table 5.

Table 5 List of project process evaluation contents, methods and tools

Content	Subject	Method	Tool
1. Completion rate of group activities by study participants	Study subjects in the intervention group	on-site observation	Record of Participation of Research Subjects in the Project Process (Annex 3)
2. Quality of the organisation and implementation of the intervention	Implementation team activities staff	on-site observation	Panel activity site quality assessment form (annex 6)
3. Satisfaction of study participants with group activities	Study subjects in the intervention group	Survey	Project Activity Satisfaction Questionnaire (Elderly) (Annex 7)
4. Household guidance and assistance in environmental rehabilitation	Staff implementing guidance on environmental improvements to households	Summary of work records	Household Environmental Assessment and Improvement Guidance Record Sheet (Annex 8)

(3) Assessment of effects

It is proposed to study the effect of the intervention at 6 and 12 months after the start of the intervention. The assessment of the occurrence of falls will be collected by filling in the monthly fall calendar; the changes in fall efficacy, knowledge, beliefs and

behaviours will be collected through on-site survey and testing.

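### Covariates are chosen by observed baseline imbalance, with no threshold, closed list or model, so adjustment for each scale score's own baseline value is not guaranteed

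*Combined protocol and SAP*

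**What the plan says.** The only covariate rule is in Section VII (2), Data collation and analysis. The candidates are "Variables such as general demographic characteristics, disease characteristics, previous falls, and level of social support at baseline"; these are "compared to see if there were any differences between the different intervention groups, and variables with differences would be corrected in the subsequent analyses". The list is illustrative, no test or cut-off defines a difference, and no adjusted model follows. Scale scores are to be compared by independent-samples t-test and falls by chi-square test, neither of which takes a covariate.

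The baseline scores exist. Section VI, 1.2.5 lists "Established scale measurements: Falls Effectiveness Scale for the Elderly, Quality of Life Scale", and Table 4 adds falls knowledge, attitude and action. At 6 months (3.2.4) the plan uses "The same assessment methods and tools as the baseline survey (Annex 5, Part IV, Part V and Part VI"), which are the knowledge, efficacy and quality-of-life parts. At 12 months, 3.3.3 says "The content of the assessment includes: the same as the baseline survey" (apart from the falls part) and 3.3.4 says "The same assessment methods and tools as the baseline survey".

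Section VI (3) mentions "the changes in fall efficacy, knowledge, beliefs and" behaviours, but as something to be collected; no change-score analysis is specified. Section III (2) sizes the trial on falls alone: "This study uses the dichotomous variable 'whether a fall occurs' as the outcome indicator". That the scales are secondary is an inference from this, since no section says so.

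**The concern.** Under random allocation, baseline differences arise by chance. Adjustment earns its keep when the covariate predicts the outcome, and an observed imbalance says nothing about that. For a repeated scale score the obvious predictor is its own baseline value, and the rule neither names it nor fixes its inclusion.

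Two things are at stake. The adjusted estimate is undefined until someone has looked at the baseline table and decided what counts as a difference. And the precision already paid for in the baseline survey may not be used for the scores.

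**Working it through.** **Plan's own figure.** With ρ = 0.17, δ = 0.35, k = 3, the formula in Section III (2) gives (1.96 + 0.84)² / (8 × [asin√0.11475 − asin√0.05525]²) = 83.5 per condition. Then 83 × 8 × 1.2052 / 0.9 = 889, against 888 stated. It reproduces and is not disputed here; it supplies the ICC of 0.0076.

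**Layout.** Section III (2) and (3): 8 conditions × 3 whole streets × 37 people. Each factor compares 12 streets with 12.

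**Assumptions, not in the documents.** Baseline-to-follow-up correlation r = 0.4, 0.5, 0.6; the falls ICC borrowed for the scores; a difference meaning p < 0.05 in a test that ignores street.

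**1. Chance that a baseline score is flagged when groups truly do not differ** (simulation):

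| Test for a difference | ICC 0 | ICC 0.0076 |
|---|---|---|
| Factor level (two groups) | 5% | 8% |
| Eight-group test | 5% | 13-14% |
| Any of 28 pairs, uncorrected | 51% | 66-67% |

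**2. Variance of a main effect if the baseline score is always included, relative to unadjusted.**
- No clustering: 1 − r² = 0.84, 0.75, 0.64, a cut of 16-36%.
- ICC 0.0076, street effects at the two times uncorrelated: [0.0076(1 + r²) + 0.9924(1 − r²)/37] / [0.0076 + 0.9924/37] = 0.91, 0.86, 0.80, a cut of 9-20%.
- ICC 0.0076, street effects correlated at r: 1 − r² again, a cut of 16-36%.

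Simulation agrees (for example 0.909, 0.858, 0.797 in the uncorrelated case). The documents do not settle which case holds.

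**3. How much of that the rule delivers.** Variance cut at r = 0.5, simulated, if the score is a candidate:

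| | ICC 0 | 0.0076, uncorrelated | 0.0076, correlated at r |
|---|---|---|---|
| Always included | 25% | 14% | 25% |
| Rule, factor-level test | 7% | 6% | 10% |
| Rule, eight-group test | 3% | 4% | 7% |
| Rule, any pair | 18% | 12% | 21% |

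The rule keeps roughly 12-43% of the gain with the first two tests (3/25 to 6/14) and 72-86% with pairwise tests (18/25 to 12/14). If the score is not a candidate, it keeps none.

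**4. Power, for scale only.** For an assumed 0.2 SD main effect at ICC 0.0076, tested on street means (22 df) with 37 per street and no loss: 71-72% unadjusted; 75-81% (uncorrelated) or 79-88% (correlated at r) with baseline always included. With the plan's 10% loss (37 × 0.9 = 33.3 per street), unadjusted power is about 68%.

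**5. False positives of the rule.** About 4-5% at ICC 0, and about 4-5% at ICC 0.0076 when the test respects street. When street is ignored at ICC 0.0076, the unadjusted test already gives about 8%, and ANCOVA that ignores street gives about 8-12%.

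**6. Falls.** Assume 17% had a fall in the past year, with risk ratio RR for falling again. Then p0 = 0.17/(1 + 0.17(RR − 1)), p1 = RR × p0, and R² = 0.17 × 0.83 × (p1 − p0)² / (0.17 × 0.83) = (p1 − p0)². For RR = 2, 2.5, 3 this is 0.021, 0.041, 0.064.

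**The case against.** The strongest reply is that the rule may include the baseline score more often than not. The plan names the independent-samples t-test and has eight groups, so pairwise testing is a natural reading. On that reading the score enters in about two thirds of trials at the plan's ICC, and most of the precision gain is kept. This stands. A reader might infer that the baseline score is usually left out, or that its precision is mostly wasted. Either holds only if the score is not a candidate, or if the baseline test is factor-level or eight-group, and the plan does not say which. The point that survives is that inclusion ranges from about 5% to 67% depending on a test nobody has specified.

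It is also fair that the size of the gain rests on assumed values of r and on an ICC borrowed from falls. A larger score ICC could shrink or remove it. In the formula of step 2, an ICC of 0.05 with uncorrelated street effects gives ratios of 1.05 at r = 0.4 and 1.12 at r = 0.6, a loss; correlated at r, the cut stays at 16-36%.

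Third, Section IX, 7.2 hides the group codes from analysts, and previous falls and demographic characteristics are already named candidates. Coding limits steering towards a favoured arm, but it does not supply a model. For falls, the change is only from conditional to fixed inclusion.

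Finally, the t-tests might be meant as tests of change. Even so, ANCOVA has variance (1 − r²)/(2(1 − r)) = (1 + r)/2 of a change-score test, or 0.70-0.80 without clustering: a further cut of 20-30%.

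**Conclusion.** The concern holds as a fault of pre-specification and efficiency. The plan leaves to the observed baseline table what a difference is, which variables are eligible and what model is fitted, so adjustment for a score's own baseline is not guaranteed. The gain from fixing it is 16-36% of variance without clustering, and 9-20% or 16-36% at ICC 0.0076, given r of 0.4-0.6 and the borrowed ICC. How much of that the rule loses depends on the unstated test: most of it with a factor-level or eight-group test, a minority with pairwise tests.

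A reader might also infer that selecting covariates this way inflates false positives. The calculations do not support that: the excess seen when street is ignored is present without any adjustment and is a separate clustering fault. For falls, the outcome that sizes the trial, past-year falls explain only about 2-6% of variance under the assumed risk ratios, so the benefit there is chiefly a model fixed in advance. Nothing here invalidates the trial.

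**What to change.** In Section VII (2), remove the statement that variables found to differ will be corrected for. In its place:

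- Analyse each scale score by ANCOVA or a longitudinal mixed model that includes its own baseline value.
- Analyse falls with a model containing any fall in the past year plus a short fixed list chosen on prognosis, for example age and sex.
- Make both models account for street; adding the baseline covariate while ignoring street does not cure the clustering fault (step 5).
- Present the baseline table descriptively, and label any imbalance-based adjustment as a sensitivity analysis.

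The cost is SAP wording only. Past-year falls, age, sex and the baseline scores are already collected (Section VI, 1.2.1, 1.2.4, 1.2.5 and Table 4). The change should be dated before the group codes are broken.
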